2.3 Statistical and Analytical Plans

2.3.1. General Considerations

Unless otherwise noted, all tests of treatment effects will be conducted at a 2-sided alpha level of 0.05; 2-sided confidence intervals will be displayed with a 95% confidence level. All tests of interactions between treatment and other factors will be conducted at an alpha level of 0.05. All analyses will follow the intent-to-treat (ITT) principle unless otherwise specified. An ITT analysis is an analysis of data by the groups to which subjects are assigned by random allocation, even if the subject does not take the assigned treatment, does not receive the correct treatment, or otherwise does not follow the protocol.

2.3.2. Analysis Populations

Baseline characteristics as well as the co-primary and secondary efficacy measures will be summarized for the ITT and per-protocol populations by treatment group and overall. Tabulations of the number and percentage of subjects included in each analysis set, by treatment group and overall, will be provided. Reasons for exclusion from analysis datasets will also be provided.

2.3.3. Patient Characteristics

The patient's age, gender, height, body weight, tobacco use, alcohol use, caffeine use, years of education, work status, time since onset of first AD symptoms, time since diagnosis, MMSE at Visit 1, APOE4 carrier status (carrier [ϵ 2/ ϵ 4, ϵ 3/ ϵ 4, ϵ 4/ ϵ 4], noncarrier [ϵ 3/ ϵ 3, ϵ 2/ ϵ 2]), APOE4 genotype (ϵ 2/ ϵ 4, ϵ 3/ ϵ 4, ϵ 4/ ϵ 4, no ϵ 4) and AChEI use at baseline will be recorded. Baseline characteristics will

be summarized for the ITT and per-protocol populations by treatment group and overall. Summaries will include descriptive statistics for continuous and categorical measures. Pearson's chi-square test will be used for treatment group comparisons of categorical data. For continuous data, t-test or corresponding non-parametric test (Mann-Whithney) will be used for the group comparing.

2.3.4. Analysis of Efficacy Outcomes

628

629

630

631

632

633

634

635

636

637

638

639

640

641

642

643

644

645

646

647

648

649

650

651

652

Normality assumption of end-points variables will be assessed by inspection of the distribution plots and by Kolmogorov-Smirnov and Shapiro-Wilk tests. Preliminary descriptive analyses will be performed by means, frequencies, standard deviations (SD) and percentages. Comparison of sociodemographic and clinical features between the study groups at baseline will be performed through ttest or Mann-Whitney tests. The longitudinal assessment of the end-points across groups will be performed through Generalized Linear Mixed Model (GLMM) for repeated measures with random intercept and random slope to account for individual differences at baseline as well as for individual change after the treatment. GLMMs will be applied to ADAS-Cog and the other efficacy outcome measures, ADCS-ADL, FAB and NPI, as dependent variables and group, time and group x time interaction as independent factors. In detail, GLMMs for Gaussian data with identity link function will be applied for ADAS-Cog, ADCS-ADL and FAB, whereas GLMM for Poisson data, with log-link function, will be used for NPI. The GLMMs on MMSE, ADAS-Cog and FAB will be adjusted for age and education. To evaluate the treatment effects on TMS/EEG data, we will use repeated-measures ANOVAs with between-subjects factor group and within-subject factors time. To evaluate the treatment effects on cortical activity, a repeated-measures ANOVA with betweensubjects factor "group" and within-subject factors "time" will be planned. Repeated-measures mixed ANOVA with between-subjects factor "group" and within-subject factors "time" will be planned to evaluate the treatment effects on oscillatory activity. Prior to undergoing ANOVA procedures, normal distribution of clinical, behavioral and neurophysiological data will be assessed

by means of Shapiro-Wilks' test. The sphericity of the data will be tested with Mauchly's test; when sphericity is violated (i.e. Mauchly's test < 0.05) the Greenhouse–Geisser correction will be used. Pairwise comparisons will be corrected by the Bonferroni method. Safety analyses for the treatment period will include comparisons between rotigotine and placebo groups by 2-sided 0.05 significance level Chi-square tests. Statistical analyses will be performed with IBM SPSS statistics, version 24.0 and R software; significance alpha level test is set up at 0.05.

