5.2. Secondary Objective

The secondary objectives of this study are as follows:

- To test the hypothesis that RTG will slow the rate of decline associated with AD in the activities of daily living, as assessed with the Alzheimer's disease Cooperative Study Activities of Daily Living (ADCS-ADL), using a GLMM for repeated measures.
 - To assess benefit of treatment with RTG on frontal cognitive functions, as demonstrated through the Frontal assessment battery (FAB), using a GLMM for repeated measures.
 - To evaluate efficacy of treatment with RTG on behavior, as demonstrated through the Neuropsychiatric Inventory (NPI), using a GLMM for repeated measures.
- To provide evidence that RTG modulates the frontal cortical activity, as evaluated in terms
 of cortical excitability and oscillatory activity evoked by single-pulse TMS during EEG,
 using a repeated-measures ANOVA. These biomarkers will be collected only in subsets of
 patients.

SECTION 6: INVESTIGATIONAL PLAN

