6.2. Timing of outcomes assessment

- 292 Preliminary screening
- Review of inclusion and exclusion criteria
- Informed consent obtained
- Demography
- Family and medical history
- Prior and concomitant medications
- Randomization and group assignment
- 299 Baseline evaluation (Day 1)
- Clinical assessment
- Neurophysiological assessment
- Post-treatment evaluation (Day 168-week 24)
- Clinical assessment
- Neurophysiological assessment

305 **6.3. Screening Phase**

306

307

308

309

310

311

312

313

314

315

316

317

At or before Visit 1, the study will be explained to the patient and caregiver. In the screening phase, all patients will undergo an extensive clinical investigation, including interviews on their medical history, a full neurological examination, the MMSE, a complete blood screening, neuropsychological assessment, neuropsychiatric evaluation, and magnetic resonance imaging. In the 30 days before entering the study, subjects will have to be clear of treatment with any drug inducing modulatory effects on the cerebral cortex excitability, such as antidepressants, benzodiazepines, anti-epileptic drugs, or neuroleptics. All AD patients will have to show a moderate level of dementia, as assessed by a neuropsychological evaluation including the MMSE (ranging from 18 to 26) and a standardized neuropsychological battery (Carlesimo et al,1996). All the patients will perform lumbar puncture for CSF biomarkers analysis for diagnostic purposes (Dubois et al., 2014). CSF t-tau and p-tau phosphorylated at Thr181 concentrations will be determined using a sandwich ELISA (InnotesthTAU-Ag, Innogenetics, Gent, Belgium) (Brem et al., 2013). Aβ1-42

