6.4. Evaluation Phase

- During the week before starting RTG/PLC administration, and during the week at the end of 24-week
- treatment, AD patients will undergo clinical assessment and neurophysiological assessment in two different
- 330 days.

318

319

320

321

322

323

324

325

326

327

340

- 1) Clinical Assessment: before and after the 24 weeks of treatment the ADAS-Cog, ADCS-ADL,
- FAB and NPI will be administered.
- 2) Neurophysiological assessment: for EEG-TMS recordings, a TMS-compatible EEG equipment
- will be used for recording EEG activity from the scalp (BrainAmp 32MRplus, BrainProducts). The
- 335 EEG will be continuously acquired from 32 scalp sites positioned according to the 10-20
- International System. TMS-EEG recordings will be performed over the left prefrontal cortex (PFC)
- and left parietal cortex (I-PPC). To precisely position the coil over the cortical sites across different
- sessions, a neuronavigation system (Softaxic, E.M.S.) will be used. During the TMS-EEG session,
- each cortical site will be stimulated with 80 single TMS pulses (ISI: 0.3 Hz) (Koch et al., 2018).

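### With only two assessments per patient, the Gaussian random-intercept and random-slope model for ADAS-Cog, ADCS-ADL and FAB is over-parameterised as usually read, and the SAP gives no covariance structure or fallback

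*Combined protocol and SAP*

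**What the plan says.** Section 2.3.4 of the SAP analyses the efficacy outcomes with a "Generalized Linear Mixed Model (GLMM) for repeated measures with random intercept and random slope to account for individual differences at baseline"; the random slope is there to capture each patient's own change under treatment. The fixed part is "group, time and group x time interaction as independent factors", with age and education added for ADAS-Cog and FAB. On the distribution for three of the scales it says: "GLMMs for Gaussian data with identity link function will be applied for ADAS-Cog, ADCS-ADL and FAB". NPI instead gets a Poisson model with a log link.

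The protocol schedules the scales twice. Section 6.4 has them given "before and after the 24 weeks of treatment the ADAS-Cog, ADCS-ADL" and the rest of the battery alike. In section 6.2 the only efficacy assessment after baseline is the "Post-treatment evaluation (Day 168-week 24" entry. Section 9.1 defines the primary measure as the change over that interval. Sections 8.1 and 9.4 mention other clinic visits, for compliance and safety, but no efficacy scale is scheduled at them.

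Section 2.3.4 names SPSS 24.0 and R without naming a package. It does not give the covariance structure of the random effects, the coding of time, the estimation method, or what to do if the model fails. For ADCS-ADL, section 5.2 states the hypothesis that "RTG will slow the rate of decline associated with AD in the activities of daily living".

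**The concern.** A random slope separates each patient's own trajectory from measurement noise. That needs more than two measurements per patient, or a restriction that the SAP does not state. With two Gaussian measurements, the slope variance and the residual variance both go into the variance of one change score.

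The specification covers the primary endpoint and two secondary endpoints. If the analyst's software refuses it, a replacement must be picked with data in hand. If the software accepts it, the reported variance components depend on the optimiser.

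**Working it through.** **Inputs.** From the documents: two assessments per patient (sections 6.2, 6.4, 9.1); random intercept and slope with a Gaussian residual (2.3.4); 47 per arm, two-sided alpha 0.05, pre-post correlation r = 0.7 and the FAB pilot figures (2.1). Assumed: correlated random effects, equal score variance at both times, and a between-arm difference of 0.42 SD of change as a yardstick. In section 2.1 the 0.42 is a one-group pre-post effect, not a between-arm one.

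**The plan's own figure.** For FAB, the SD of the difference is √(4.43² + 4.48² − 2 × 0.7 × 4.43 × 4.48) = √11.91 = 3.451. The effect size is (12.32 − 10.85)/3.451 = 0.426. The exact paired t-test has power 0.807 at n = 46, so the SAP's n = 46 is reproduced.

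**Parameter count.** Code time 0/1, with intercept variance a, slope variance b, covariance c and residual variance s. The two assessments give three moments:

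- V11 = a + s
- V12 = a + c
- V22 = a + 2c + b + s

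Four unknowns, three equations, rank 3. Adding k to s and to c, taking k from a and 2k from b, changes none of the three.

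**Numerical check.** On one simulated data set (47 per arm; V11 = 52.54, V12 = 46.70, V22 = 75.54):

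| s | a | c | b | REML log-likelihood | group × time (SE) |
|---|---|---|---|---|---|
| 1 | 51.54 | −4.84 | 32.68 | −616.947 | −0.9945 (1.2148) |
| 8 | 44.54 | 2.16 | 18.68 | −616.947 | −0.9945 (1.2148) |
| 15 | 37.54 | 9.16 | 4.68 | −616.947 | −0.9945 (1.2148) |

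The slope variance can be 33 or 5 with the same likelihood. The treatment contrast does not move. It equals the between-arm difference in change scores, with SE √[(52.54 + 75.54 − 2 × 46.70) × 2/47] = √(34.68 × 2/47) = 1.215.

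**Other readings of the SAP sentence.**

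- Uncorrelated effects, baseline coded 0: three parameters, rank 3, just identified. Here b = V22 − V11, so week-24 variance cannot be below baseline variance.
- Uncorrelated effects, time centred at −0.5/+0.5: three parameters, rank 2, not identified.

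**Software, on simulated 94 × 2 data.** The lme4 package stops on the correlated model because 188 observations do not exceed 188 random effects. It fits the uncorrelated version. The nlme package and Python's statsmodels return a fit to the correlated model, but nlme cannot give intervals for the variance components. SPSS was not tested.

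**ANCOVA against the change score.** Per unit of score variance, the change score has variance 2(1 − r) = 2 × 0.3 = 0.60. ANCOVA has residual variance 1 − r² = 1 − 0.49 = 0.51. The ratio is 0.51/0.60 = 0.85, or (1 + r)/2 in general.

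- Change score: noncentrality 0.42 × √(47/2) = 2.036; power 52% by the exact t-test, 53% by the normal approximation and by simulation.
- ANCOVA: standardised difference 0.42/√0.85 = 0.456; noncentrality 0.456 × √(47/2) = 2.21; power 59%.
- Putting r = 0.5 or 0.9 into (1 + r)/2 gives ratios 0.75 or 0.95 and ANCOVA power 64% or 54%.

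**What a late choice could do.** In 20,000 simulated trials under these assumptions, ANCOVA and the change-score test disagreed on p < 0.05 in 13% of trials at the 0.42 difference. Under the null each rejected about 5%; taking whichever was significant rejected 6.8%.

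**The case against.** The strongest reply is that the treatment test is sound. With complete data, every mixed-model covariance tried (correlated slope, uncorrelated slope, random intercept only) gives the same group-by-time estimate and SE. This stays true with age and education as main effects. With an assumed 15% missing at week 24, the estimate moved by at most 0.04 against an SE of about 1. Only a nuisance variance split is undetermined, and the SAP never says that the effects are correlated. All of this stands.

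A reader might therefore infer too much in three ways.

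- **That the primary analysis cannot be fitted.** The documents do not support this. The refusal is one R package's default check, other software returns a usable contrast, and one permissible covariance structure is just identified.
- **That the treatment effect is biased.** It is not, for the reasons above.
- **That NPI has the same fault.** The Poisson model has no free residual variance, so the count does not apply to it. Cutting it to a random intercept for consistency could understate visit-to-visit variation and raise false positives.

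What the reply does not meet is the missing specification. Whether the model runs, and with what variance components, depends on choices that the SAP leaves open. Swapping one mixed-model covariance for another would barely matter, but nothing limits a late replacement to that family.

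**Conclusion.** The point holds as a specification defect in the primary model, shared by ADCS-ADL and FAB. Under the usual correlated structure the model asks for four covariance parameters from three moments, and the SAP supplies neither a structure that would resolve this nor a fallback. The damage is to pre-specification, not to the estimate of effect.

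Separately, the planned model reduces to a change-score contrast. ANCOVA uses the same data with 15% less variance at r = 0.7, worth about 6 to 7 percentage points of power at the yardstick difference. That gain rests on the SAP's correlation and on equal variances at the two times; it shrinks as r rises towards 1.

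The wording of the ADCS-ADL objective is a lesser matter. Two assessments cannot tell a slower rate from a constant shift. For the primary endpoint, sections 5.1 and 9.1 already speak of the state or change at 24 weeks.

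**What to change.** In section 2.3.4, for ADAS-Cog, ADCS-ADL and FAB:

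- Remove the random slope and name one primary model. Preferred: ANCOVA of the week-24 score on baseline score and group, with age and education for ADAS-Cog and FAB as already planned.
- The alternative is a two-assessment repeated-measures model with an unstructured 2 × 2 covariance and no random slope. With separate baseline means per arm and complete data it gives the change-score contrast, so it resolves the identifiability problem without the ANCOVA gain.
- State the software routine, the fallback if a model fails to converge, and how patients without a week-24 score enter the analysis. ANCOVA does not use them unless a rule is given.

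Leave the NPI Poisson model with its random slope. Optionally, reword the ADCS-ADL objective in section 5.2 as a between-arm difference in change at week 24.

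The cost is a few sentences in the SAP, settled before unblinding. No new data or visits are needed.

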6.5. Treatment Phase

- After recruitment and baseline assessments, AD patients will be assigned to RTG or PLC as add on
- to current AChEI therapy (donepezil or rivastigmine). We will use the Neupro® (Rotigotine
- 343 Transdermal System), a transdermal delivery system that provides rotigotine, a non-ergolinic DA

agonist, currently used for treatment of Parkinson's disease. When applied to intact skin, Neupro is designed to continuously deliver rotigotine over a 24-hour period. The precise mechanism of action of rotigotine, as a treatment for Parkinson's disease, is unknown although it is suggested to be related to its ability to stimulate D2 receptors within the brain. All of the non-ergoline agonists currently in clinical use are able to bind and activate the D2-like family of dopamine receptors, although they differ in their relative efficacy at these receptors. In preclinical studies, rotigotine has been already shown to act as a strong dopamine D2 receptor agonist (Van der Weide *et al.*, 1987; Tan, 2003). Moreover, in radioligand binding studies (Scheller *et al.*, 2009), rotigotine exhibited high affinity for the dopamine D3 receptor (Ki 0.71 nM), D2, D5 and D4 receptors (Ki 4–15 nM) and low affinity for the dopamine D1 receptor (Ki 83 nM). Furthermore, the continuous and uniform release of rotigotine from the transdermal delivery system has been demonstrated to give stable plasma drug levels over 24 h, providing a relatively continuous, more physiological, stimulation of dopamine receptors, with potential greater benefits on disease symptoms.

All treatments will be administered for 24 weeks with no interruptions. All treatments will be administered for 24 weeks with no interruptions. Rotigotine will be administered through a 4 mg transdermal patch (Neupro, UCB pharma), after having started with a 2 mg patch for 1 week. Transdermal patches of rotigotine have a release surface area of 10 or 20 cm² and contain 4.5 or 9 mg of rotigotine to release respectively 2 or 4 mg during a 24-hour period when applied to intact skin. The placebo transdermal patch contained in cardboard packaging will be identical to the rotigotine except for the absence of rotigotine.

SECTION 7: STUDY POPULATION

- Eligible patients will be males and females with mild to moderate AD, as specified in the entry
- 369 criteria that follow. Entered patients who meet all of the inclusion criteria and are not excluded by

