2. STATISTICAL ANALYSIS PLAN

2.1. Determination of Sample Size

A total of 94 randomly assigned patients (47 per group) were planned on the basis of our previous study in which we assessed the effects of rotigotine on cortical plasticity and cognitive functions in a small sample of Alzheimer's disease patients (Koch et al., 2014). In that pilot study, a significant (although unpowered) difference was observed in pre-post (12 weeks) treatment with rotigotine in n=7 patients in both the cognitive measures MMSE (mean pre=21.73, SD=4.14; mean post=23.23, SD=3.93) and in FAB (mean pre=10.85, SD=4.43; mean post=12.32, SD=4.48). Treatment duration of the present study is twice larger than the one of the pilot study thus a larger effect size is expected. However, for precautionary reasons, we consider the same effect sizes found in the previous work (equal to 0.48 for MMSE and equal to 0.42 for FAB computed as post-pre means over standard deviation of difference post-pre), for the sample size calculation of the present study. In detail, adopting a two-tailed paired t-test, with type I error alpha=0.05 and a plausible correlation between pre-post measured variables of 0.7, the FAB effect size equal to 0.42 requires a minimum sample of n=46 for reaching a power of 0.8. For MMSE, this sample size allows to reach a power of 0.9. The minimum total sample size was then augmented up to N=92 considering the matched placebo group.

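### With two visits, the primary mixed model reduces to an unadjusted comparison of mean change; conditioning on baseline ADAS-Cog would be more precise at no cost

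*Combined protocol and SAP*

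**What the plan says.** Protocol 6.4 schedules the clinical scales twice: "before and after the 24 weeks of treatment the ADAS-Cog, ADCS-ADL", FAB and NPI. Protocol 9.1 defines the primary measure as the change in ADAS-Cog from baseline to week 24.

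SAP 2.3.4 fits mixed models with "group, time and group x time interaction as independent factors" and with "random intercept and random slope to account for individual differences at baseline as well as for individual change after the treatment". On the distribution it says "GLMMs for Gaussian data with identity link function will be applied for ADAS-Cog, ADCS-ADL and FAB"; NPI gets a Poisson model with log link. On covariates it says "The GLMMs on MMSE, ADAS-Cog and FAB will be adjusted for age and education". The TMS-EEG measures go to repeated-measures ANOVAs with group and time.

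Nowhere is baseline ADAS-Cog a covariate, a common baseline mean imposed on the two arms, or an age x time or education x time term named. SAP 2.3.5 adds only unnamed confounders, to be examined in separate ad-hoc models.

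**The concern.** The model looks like a covariate-adjusted longitudinal analysis, but two visits leave it little to work with. Each arm has its own free baseline mean, so the treatment contrast uses only each patient's change. Age and education are constant within a patient, so as main effects they shift both visits equally and drop out of the change. The random intercept and slope describe covariance within patients. They do not adjust the contrast for arms that happen to start at different ADAS-Cog levels.

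Two things are at stake. The trial collects a baseline score that could give a tighter estimate than differencing does. And the primary result would be described as adjusted for age and education when numerically it is close to unadjusted.

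**Working it through.** **Inputs.** Two visits (protocol 6.4). 47 patients per arm, two-sided alpha 0.05, and a "plausible correlation between pre-post measured variables of 0.7" (SAP 2.1). The standardised effect 0.42 is the pilot's pre-post FAB effect (SAP 2.1). The documents give no between-arm effect and no correlation for ADAS-Cog, so using 0.42 and 0.7 for it is an assumption.

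**The plan's own figure.** From the pilot FAB SDs, the SD of the difference is sqrt(4.43² + 4.48² − 2 × 0.7 × 4.43 × 4.48) = 3.451, and 1.47/3.451 = 0.426. A paired t-test at 80% power then needs n = 46, as stated (47 if 0.42 is used as rounded). MMSE power at n = 46 with effect 0.48 is 0.89 by exact t and 0.90 by normal approximation, against the stated 0.9. The SAP's arithmetic reproduces.

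**Why the covariates cancel.** Let patient i have mean a + b·group + c·age + e·education at baseline, and the same plus t + d·group at week 24. The mean change is t + d·group, free of age and education. Whatever the within-patient covariance, the two scores can be rewritten as the change and a second combination uncorrelated with it. That second combination has its own free intercept, group and covariate terms, so with complete data it carries no information on d. The estimate of d is the difference in mean change.

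**Numerical check** on one simulated data set (94 patients, complete data, with age and education affecting both visits equally):

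| Model | Estimate | SE |
|---|---|---|
| Mixed model, no covariates | −1.2152 | 1.3956 |
| Mixed model, age + education | −1.2152 | 1.3956 |
| Least squares on change | −1.2152 | 1.3956 |
| Mixed model, plus age x time and education x time | −1.2018 | 1.4151 |
| ANCOVA on baseline | −0.9428 | 1.2497 |
| ANCOVA on baseline, age, education | −0.5224 | 1.1970 |

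A separate check with a fixed unstructured covariance gave 0.7848 (SE 1.3699) with and without covariates. Covariate x time terms alone moved the estimate but did not improve precision here; conditioning on baseline did. With 15% of week-24 values missing, the mixed model moved slightly, from −1.596 (SE 1.478) to −1.578 (SE 1.466).

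**Size of the loss.** With equal visit variances and correlation r, the variance per patient relative to a week-24-only comparison is 2(1 − r) for change and 1 − r² for ANCOVA. The ratio is (1 + r)/2. At r = 0.7 this is 0.51/0.60 = 0.85. A simulation of 20,000 trials gave 0.87, which includes the small-sample cost of estimating the slope.

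**Power** at 47 per arm comes from the noncentral t distribution with noncentrality 0.42 × sqrt(47/2) = 2.04 for change. For ANCOVA at r = 0.7 it is (0.42/sqrt(0.85)) × sqrt(47/2) = 2.21.

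| r | Variance ratio | 47 per arm is worth | Power, change | Power, ANCOVA |
|---|---|---|---|---|
| 0.5 | 0.75 | 62.7 | 0.52 | 0.64 |
| 0.7 | 0.85 | 55.3 | 0.52 | 0.59 |
| 0.9 | 0.95 | 49.5 | 0.52 | 0.54 |

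**The case against.** The declared endpoint is change from baseline, and the planned contrast estimates it validly, so ANCOVA may be called a preference. It is true that the analysis is not invalid. But with baseline in the model, taking the week-24 score or the change as response gives the same treatment coefficient, so conditioning does not abandon the endpoint.

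Several stronger readings are tempting, and the documents do not support them:

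- A reader might infer that the plan uses the least efficient valid estimator, or throws the baseline away. At r = 0.7 the variance factors are 1.00 for week 24 alone, 0.60 for change and 0.51 for ANCOVA, so differencing already captures most of the gain. Change is worse than week 24 alone only if r is below 0.5.
- A reader might infer bias from regression to the mean. The arms are randomised, so the contrast is unbiased on average. What remains is a chance baseline difference in this one trial. Balancing on screening MMSE (protocol 6.1 and 8.1, though SAP 2.2 lists only age, sex and APOE) would reduce that risk, but MMSE is not ADAS-Cog.
- A reader might infer that the adjustment can never have any effect. Exact cancellation needs complete data and main-effect covariates. The latter is the plain reading, not an explicit statement. With dropout the covariates move the result a little.
- A reader might extend the cancellation to every outcome. Age and education adjustment is not promised for ADCS-ADL or TMS-EEG, and the Poisson NPI model is outside the argument.
- A reader might think ANCOVA must wait until the order of events is settled: 6.2 lists "Randomization and group assignment" ahead of the baseline evaluation, while 6.5 says "After recruitment and baseline assessments, AD patients will be assigned to RTG or PLC as add on". Under 6.4 baseline is measured before dosing, and under SAP 2.2 allocation is held centrally and blind. Treatment cannot affect the baseline score in either order, so the fix does not depend on this.

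**Conclusion.** The point holds as one of efficiency and accurate reporting, and it is a free improvement. For complete two-visit data, the Gaussian models for ADAS-Cog and FAB deliver the difference in mean change, with an SE that age and education leave essentially unchanged. No other section, including SAP 2.3.5, repairs this.

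The gain from conditioning on baseline is 15% of variance if r = 0.7 carries over from MMSE/FAB to ADAS-Cog over 24 weeks and the visit variances are equal. It is 25% at r = 0.5 and only 5% at r = 0.9. The power figures also rest on an effect borrowed from a within-arm FAB change and are illustrative. The cancellation itself rests on none of these assumptions.

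**What to change.** In SAP 2.3.4, make the primary analysis an ANCOVA of week-24 ADAS-Cog with group, baseline ADAS-Cog, age and education. To keep patients without a week-24 value, specify instead a constrained longitudinal model: one common baseline mean for both arms, a group effect at week 24 only, and age x time and education x time terms. State which coefficient is the treatment effect.

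Use the same form for FAB. For ADCS-ADL and the TMS-EEG measures, condition on the baseline value likewise. NPI needs its own consideration and is not covered here. If the current model is kept as a supplementary analysis, describe it as a comparison of mean change rather than as adjusted for age and education.

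The cost is SAP wording and a few degrees of freedom. No data, visits or patients are added.

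### SAP 2.3.4 names a repeated-measures model on MMSE and 2.1 quotes a power of 0.9 for MMSE, but no MMSE is scheduled after screening and it is not a declared outcome

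*Combined protocol and SAP*

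**What the plan says.** SAP 2.3.4 describes mixed models with group, time and group-by-time terms. It first names the outcomes to be modelled: "GLMMs will be applied to ADAS-Cog and the other efficacy outcome measures, ADCS-ADL, FAB and NPI, as dependent variables". It then assigns distributions. The Gaussian part reads "GLMMs for Gaussian data with identity link function will be applied for ADAS-Cog, ADCS-ADL and FAB", and NPI gets a Poisson model with log link. MMSE is in neither list. The next sentence nevertheless reads "The GLMMs on MMSE, ADAS-Cog and FAB will be adjusted for age and education".

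Protocol 6.4 gives the clinical battery in one list: "before and after the 24 weeks of treatment the ADAS-Cog, ADCS-ADL", continuing "FAB and NPI will be administered". MMSE is not in it. Protocol 6.3 places MMSE in the screening work-up ("full neurological examination, the MMSE, a complete blood screening").

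Protocol 9.1 names ADAS-Cog as the primary measure. Protocol 9.2 names FAB, ADCS-ADL, NPI and the TMS-EEG markers as secondary. The objectives in 5.1 and 5.2 name the same set.

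SAP 2.1 bases the sample size on pilot changes in MMSE and FAB. After deriving n = 46 from FAB, it adds: "For MMSE, this sample size allows to reach a power of 0.9".

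**The concern.** A repeated-measures model with a group-by-time term needs at least one post-treatment value of its outcome. Under 6.4 there is none for MMSE, so one named efficacy analysis has no data to run on. It also has no stated distribution or link and no place among the declared outcomes.

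Two things are at stake. First, if MMSE values at week 24 do exist, the sentence in 2.3.4 would allow an efficacy test at 0.05 on an outcome never declared in section 9. Its standing would be unclear: SAP 2.3.2 speaks of co-primary measures although 9.1 names only one, and the Bonferroni correction in 2.3.4 covers pairwise comparisons, not multiple outcomes. Second, the higher of the two powers quoted in 2.1 belongs to a scale that the trial does not follow up, which makes the sizing look better supported than it is.

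**Working it through.** **1. Where MMSE appears.**

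| Place | Role of MMSE |
|---|---|
| Protocol 4 | result of the earlier pilot work |
| Protocol 5 (opening), 6.1, 6.3, 7.1 | screening range or eligibility |
| Protocol 6.1, 8.1 | screening severity as a randomisation factor |
| Protocol 5.1, 5.2 (objectives) | absent |
| Protocol 6.4 (before/after battery) | absent |
| Protocol 9.1, 9.2 (outcome measures) | absent |
| SAP 2.1 | pilot effect size and power |
| SAP 2.3.3 | Visit 1 characteristic |
| SAP 2.3.4, outcome and link lists | absent |
| SAP 2.3.4, adjustment sentence | dependent variable of a GLMM |

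The documents schedule one MMSE occasion and no post-treatment value. With one occasion, neither a pre-post difference nor a group-by-time term can be estimated.

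**2. Reproducing the 0.9.** Inputs from SAP 2.1: MMSE pre 21.73 (SD 4.14), post 23.23 (SD 3.93); correlation 0.7; two-tailed paired t-test; alpha 0.05; n = 46.

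- SD of change = √(4.14² + 3.93² − 2 × 0.7 × 4.14 × 3.93) = √(17.140 + 15.445 − 22.778) = √9.806 = 3.131
- d = (23.23 − 21.73) / 3.131 = 1.50 / 3.131 = 0.479 (stated 0.48)
- Noncentrality = 0.48 × √46 = 3.256. Exact paired-t power is 0.890; the normal approximation gives 0.902 (stated 0.9).

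The figure reproduces as a pre-post test within a single arm of 46.

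**3. The FAB figure from the same section.** FAB pre 10.85 (SD 4.43), post 12.32 (SD 4.48).

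- SD of change = √(19.625 + 20.070 − 27.785) = √11.910 = 3.451
- d = 1.47 / 3.451 = 0.426 (stated 0.42)
- n for power 0.8 is 46 with d = 0.426 and 47 with d = 0.42 (stated 46).

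This also reproduces, and it is the same kind of test: within one arm. FAB, with the smaller effect, sets n = 46. The MMSE power is then read off at that n.

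**4. Illustration of between-arm power.** Assumptions not in the documents: no mean change on placebo, and the same SD of change in both arms. For a two-sample t-test the noncentrality is d × √(n/2), with n per arm. For MMSE at 46 per arm this is 0.48 × √23 = 2.302.

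| d | 46 per arm | 47 per arm | 50 per arm |
|---|---|---|---|
| 0.48 (MMSE) | 0.62 | 0.63 | 0.66 |
| 0.42 (FAB) | 0.51 | 0.52 | 0.55 |

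The arm sizes are the three that the documents imply: N = 92, N = 94, and about 100. Under these assumptions, power 0.9 at d = 0.48 would need about 92 per arm.

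**The case against.** The best defence is that MMSE is a stray word. The two sentences before it in 2.3.4, the objectives, 6.4 and section 9 all agree on an outcome set without MMSE. No declared outcome loses its data or its model, and the ADAS-Cog analysis is untouched. This stands as a limit on severity. It does not make the text right: MMSE is also one of the two scales on which 2.1 rests, and a prespecified plan should not name an efficacy model that its own schedule cannot feed.

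A reader might infer more than the documents support, in four ways:

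- **That 0.9 is the power of the MMSE GLMM.** It is not. SAP 2.1 ties it to a paired t-test, and no power is stated for any GLMM.
- **That MMSE is known never to be measured after screening.** The documents show only that it is not scheduled. Protocol 6.2 lists a week-24 clinical assessment without itemising it, and section 3 refers to a study schedule that is not in the text supplied. Protocol 6.4 does itemise the battery, so the plan as written still has no such value.
- **That the sample size depends on MMSE.** It does not. Removing the MMSE figure leaves n = 46 per arm unchanged.
- **That leaving ADCS-ADL and NPI out of the age and education adjustment is a mistake.** The three scales named are the cognitive tests and the two omitted measure daily living and behaviour, so the split may be deliberate. SAP 2.3.5 also provides for a separate look at confounders.

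It is also fair to object that striking only the MMSE power would leave 2.1 resting on a FAB figure with the same defect. That is correct, and both figures need the same label.

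**Conclusion.** The inconsistency is real and sits in operative text. SAP 2.3.4 names an adjusted repeated-measures model on MMSE for which the plan schedules no post-treatment observation, declares no outcome and gives no link. The 0.9 in 2.1 is arithmetically sound (0.890 recomputed) but is a within-arm figure for a scale that is not followed up. It therefore supports no outcome and no between-arm comparison. The FAB 0.8 does concern a declared secondary outcome, but it too is a within-arm figure.

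The primary analysis and N are not affected by this point. The conclusion about MMSE rests on reading the list in 6.4 as complete. The between-arm powers (0.62 to 0.66 for d = 0.48; 0.51 to 0.55 for d = 0.42) rest on the two added assumptions and show only that the within-arm figures do not carry over to a comparison of arms.

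**What to change.** Settle the following before unblinding.

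1. **SAP 2.3.4.** Either delete MMSE, so that the sentence covers ADAS-Cog and FAB only; or, if MMSE was intended, add it at baseline and week 24 in 6.4, list it as a secondary measure in 9.2, and give its distribution and link in 2.3.4. If patients have already completed week 24 without an MMSE, only deletion remains.
2. **SAP 2.1.** Remove the 0.9, or state that it is a within-arm pre-post figure from the pilot that supports no trial endpoint. Label the FAB 0.8 as within-arm in the same way.
3. **Optional.** Age and education could be added to the ADCS-ADL and NPI models, since 6.1 lists both as randomisation factors. This is a choice, not the correction of an error. If it is not made, one sentence giving the reason for adjusting only the cognitive scales would help.

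Deletion and relabelling cost wording only, and N stays as it is. Keeping MMSE costs one more scale at two assessments and one more declared secondary test. Neither route supplies a between-arm power for ADAS-Cog. SAP 2.1 gives none, and that gap needs separate treatment.
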